6 STUDY SCHEDULE

Study Activity		Time Points						
		Pre-op/Baseline	Surgery	Two week post op (\pm 7 days)	6 weeks post op (\pm 7 days)	26 weeks (\pm 7 days)	1 Year (- 8 weeks + 12 weeks)	2 Year (-8 weeks + 12 weeks)
Signed Consent Form		X						
Review of Medical History Demographics/Diagnosis		X						
Inclusion/Exclusion Criteria form		X	X					
Randomization form			X					
Surgical details form			X					
Clinical Assessments	MRI	SOC				X		
	Rotator Cuff Assessment and Healing Index	X				X		
	Radiograph AP View or Bone Mineral Density Scan	SOC						
	ASES Range of Motion	X				X	X	
Patient Surveys	ASES	X				X	X	X
	VAS	X		X	X	X	X	X
	VR-12	X				X	X	X
	SANE	X				X	X	X
WHOOOP Management*		X**		X	X	X		
Assessment of Adverse Events			As occurs					

* for selected sites only

**Whoop set up and patient instruction for use

Diagnosis and intra-operative data will be obtained and will include but not be limited to the type and size of the rotator cuff tear.

Shoulder range of motion (ROM) in forward flexion, external rotation at the side, external rotation at 90° of abduction, and internal rotation at 90° of abduction will be measured with a goniometer. Internal rotation will also be estimated to the nearest spinal level. The lead investigator or assigned research staff at each site will perform all measurements.

6.1 Radiograph

The MRI imaging will be collected according to standard of care pre-operatively and then at the 26 ± 2 weeks timepoint.

6.2 MRI Sequence and Outcomes

A standard shoulder MRI protocol utilizing a minimum of a 1.5 Tesla magnet shall be utilized. A recommendation for setting is: 5 pulse sequences, sagittal oblique T1-weighted and fast spin echo (FSE) T2-weighted with fat saturation, axial FSE proton density and FSE T2-weighted with fat saturation, and coronal oblique FSE T2-weighted with fat saturation. Post-operative cuff integrity will be classified utilizing the 5 categories described by Sugaya et al¹⁰ type I, sufficient thickness with homogeneously low intensity; type II, sufficient thickness with partial high intensity; type III, insufficient thickness without discontinuity; type IV, presence of a minor discontinuity; type V, presence of a major discontinuity.

[figure not shown]
6.3 WHOOP Wearable Strap

For selected sites utilizing the WHOOP wearable strap: Continuous general health data will be recorded with a WHOOP device. The WHOOP device will be provided to each patient at select sites prior to surgery. This device is worn on the wrist continuously and provides real-time data that is transmitted wirelessly and will be worn by the patient for six months post-operatively. Data includes general health measures such as heart rate, respiratory rate, sleep, and activity levels. For example, total sleep duration and REM sleep duration will be compared between groups to assess whether or not patient sleep is improved with DAA in the postoperative period.

6.4 Rotator Cuff Healing Index

For the Rotator Cuff Healing Index score, if a DXA scan is not available for bone mineral density determination, an AP radiograph of the target shoulder will be used for evaluation and measured as follows.

The first level is the most proximal point on the humerus where the outer medial and lateral cortical borders become parallel. A perpendicular line will be drawn from the medial outer cortex of the humerus to the lateral outer cortex of the humerus and measured with a digital caliper to provide the thickness of the entire bone (M1). At the same level, a measurement of the width of the intramedullary canal will be obtained (M2). The M2 distance was then subtracted from M1 to obtain the combined cortical thickness at level 1 (C1). The second level measurements were obtained 20 mm distal to level 1. The same methods were used to calculate the combined cortical thickness at this second level (C2). The C1 and C2 values were then averaged to determine the CBT_{AVG} for each patient. Denote the parallelism of the outer proximal humerus cortex at levels 1 and 2 if the bone thickness measurements are not more than 1.0 mm different between levels.¹¹

Cortical thickness average:

- If ≥ 6 mm - score = 0
- If < 6 mm - score = 2

7 MONITORING

Based on human subject risk, size, nature, and complexity this study is considered to be minimal risk. . The product has been cleared for sale and Arthrex has not identified any additional device risks during its time on the market. Therefore, the study will be monitored using a risk-based approach, including periodic monitoring calls with site staff and when necessary on-site visits. The EDC system will be reviewed periodically by the sponsor, or designee, for remote data queries, missing data, and data inconsistencies.

Sponsor will have the right, upon reasonable notice and during regular business hours, to audit the documents of the study. The Site and Investigator will cooperate with Sponsor or designee and will make all study documents including informed consent documents, HIPAA authorizations, and study data available. Sponsor will communicate findings to the Site in an exit meeting or in writing. The Site and Principal Investigator must correct or explain any deficiencies noted by the Sponsor.

The Sponsor will collect all site staff's essential documents, record of training, and delegation of authority logs. New members of the site study team may be added from time to time and should only start their assignments after receiving adequate training.

When findings indicate that retraining is required, Arthrex, or designee, must retrain site staff as soon as possible. Source verification on-site will be performed when risks are triggered by issues identified during central data review. Sites are subject to CAPA and Root Cause Analysis to address outstanding or inconsistent data and/or protocol deviations.

8 ADVERSE EVENTS

8.1 Adverse Events

An adverse event (AE) is any undesirable experience (e.g., sign, symptom, illness, clinically significant abnormal laboratory value, or other medical event) occurring in a subject during the course of the study, whether or not it is related to the study device or procedure.

Due to the minimal risk of the study, only device related adverse events or events that impact the study outcomes will be reported in the electronic data capture (EDC) system. The Sponsor is responsible for the classification for AE's and ongoing safety evaluation

for the products. All related AEs shall be classified by relatedness, event type, and serious or non-serious. The Sponsor shall review the PI's assessment of all AEs. In the case of disagreement between Sponsor and PI, the Sponsor shall communicate both opinions to medical monitor.

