3.2 Potential Risks and Benefits

3.2.1 Potential Risks

Potential risks from the surgery are equivalent to standard surgery and will be discussed with the patient as standard of care.

Potential risks related to the DAA include possible allergic or host reaction to the allograft. However, these risks are minimal.

Treatment risks are standard procedure risks that are discussed as part of orthopedic care. These include:

- Infections, both deep and superficial
- Allergies or other reactions to device materials
- Temporary or permanent nerve damage as a result of pressure or hematoma.
- Loosening of the implant or tissue reaction to implant
- Dislocation, subluxation, or inadequate scope of movement as a result of failure to achieve optimum positioning of the implant.
- Bone fractures as a result of one-sided overload or weakened bone structure.
- Allergic reaction to allograft or residual allograft processing reagents

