4.4 Randomization Procedures

Randomization shall be performed during surgery after intra-operative inclusion/exclusion eligibility has been met, using computer-generated randomization. Patients will be randomized to have either the addition of DAA following a standard rotator cuff repair (DAA Group) or standard Rotator Cuff repair without DAA (Control group).

Intra-operative exclusion criteria:

1. Partial rotator cuff repairs
2. Lafosse grade 3 or higher subscapularis tears

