5.2 Study Procedures

The surgery is performed as standard of care. Surgeons are advised to review the product-specific surgical technique prior to performing any surgery. Arthrex provides detailed surgical techniques in electronic formats on the Arthrex website.

The rotator cuff will be repaired per each surgeon's preferred method, documenting the number of anchors and usage of single-row or double-row repair.

[figure not shown]
Tears with sufficient mobility to cover the greater tuberosity will be repaired with a knotless double-row technique with a minimum of 4 anchors (SpeedBridge™; Arthrex, Inc.)

In the study group, DAA will be performed with a 1 mm acellular dermal allograft (CuffMend™ graft; Arthrex Inc., Naples, FL) (Figure 1). The DAA is designed to augment the rotator cuff repair. The DAA will be inserted through a portal with a graft spreader. The graft is then secured into the medial rotator cuff tissue. The graft spreader is removed. Finally, the graft is secured into the lateral greater tuberosity with two knotless anchors (3.5 mm PushLock®; Arthrex, Inc.)

Medial graft fixation will be performed with FiberStitch™ RC (Arthrex Inc.) based on surgeon preference. In the FiberStitch™ technique a minimum of two anchors will be used to secure the allograft to the medial tissue. Tears with limited tendon mobility in which only a single-row repair can be performed will be repaired with a knotless technique using inverted mattress FiberTape sutures (Arthrex, Inc) and a medial looped suture (Knotless Ripstop; Arthrex Inc.)

Postoperatively the patient will be placed in a sling for six weeks with hand, elbow, and wrist range of motion only. At six weeks, the sling will be removed, and passive range of motion will be initiated. At nine weeks, active motion will be initiated. At 12 weeks, postoperative strengthening will be allowed. Full activities will be permitted at six months postoperative.

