8.3 Adverse Event Documentation

The Principal Investigator or designee will report related adverse events for the study analysis. Adverse events will be evaluated and differentiated by:

- Severity of the event defined below.
 - Mild: Awareness of signs and symptoms, but easily tolerated; are of minor irritant type, causing no loss of time from everyday activities; symptoms would not require medication or a medical evaluation; signs and symptoms are transient.
 - Moderate: Discomfort severe enough to cause interference with usual activities; requiring treatment, but not extended hospitalization or intensive care for the subject.
 - Severe: Incapacitating with the inability to do work or normal activities; signs and symptoms may be systemic in nature or require medical evaluation and treatment; requiring additional hospitalization or intensive care (prolonged hospitalization).

- The following clarifications are provided for the serious adverse events:
 - Life-threatening means that the subject was, in the view of the Investigator, at immediate risk of death from the event as it occurred. The definition does not include an event that, had it occurred in a more severe form, might have caused death.
 - Hospitalization for elective treatment of a pre-existing condition that did not worsen during the study is not considered a serious adverse event.
 - “Inpatient” hospitalization means the subject has been formally admitted to a hospital for medical reasons. This may or may not be overnight. It does not include presentation at a causality or emergency room.
 - Important medical events that may not result in death, or be life-threatening, however, based upon appropriate medical judgment, may jeopardize the subject, and may require medical or surgical intervention to prevent one of the outcomes listed in this definition.
 - Is significant for any other reason.

- Relatedness to the device or procedure, defined as:
 - Unrelated: AE is due to the underlying disease state or concomitant medication, or therapy not related to the study-specific devices or procedures.
 - Probably not Related: AE had minimum or no temporal relationship to the study-specific devices or procedures, and more likely alternative etiology exists.
 - Possibly Related: AE had a strong temporal relationship to the study-specific devices or procedures and alternative etiology is equally or less likely compared to the potential relationship to the study-specific devices or procedures.

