9 STATISTICAL CONSIDERATIONS

The study is a post-market clinical follow-up study. Given the observational nature of the study a sample size calculation was not performed. The total enrollment goal of 120 subjects was selected in an effort to create a generalizable sample that is large enough to provide sufficient data on safety and performance. Outcomes recorded at specific time points will be analyzed according to standard measures of descriptive statistics. The number of dropouts and withdrawals will be presented. Interim analyses may be conducted based on regulatory request. After completion of the study, a final report encompassing all study data will be generated.

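### The adverse event entry rule in Section 8.1 turns partly on device relatedness while the graft is used in one arm only, so recorded counts by arm could be distorted; 8.1, 8.1.1 and 8.3 need one arm-neutral rule.

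*Combined protocol and SAP*

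**What the plan says.** Section 8.1 defines an adverse event broadly, as any undesirable experience "whether or not it is related to the study device or procedure". It then narrows what is collected: because the study is considered minimal risk, "only device related adverse events or events that impact the study outcomes will be reported in the electronic data capture (EDC) system". The sponsor classifies events and reviews the investigator's assessments, and disagreements go to a medical monitor.

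Two other sections describe the scope differently. Section 8.1.1 has serious events entered if they are applicable, a word it does not define. Section 8.3 has the investigator or a designee report related events for the analysis, on a scale headed "Relatedness to the device or procedure, defined as".

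On the devices, Section 5.2 gives the DAA arm a dermal graft with medial fixation, and "the graft is secured into the lateral greater tuberosity with two knotless anchors". The underlying repair also uses implants: tears with enough mobility are "repaired with a knotless double-row technique with a minimum of 4 anchors". Section 3.2.1 says that "Potential risks related to the DAA include possible allergic or host reaction to the allograft", and lists infection, nerve damage, implant loosening and fracture as risks of treatment generally.

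Section 9 justifies the 120 subjects as a sample "large enough to provide sufficient data on safety and performance". Sections 9.2 to 9.5 contain no adverse event analysis.

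**The concern.** Under Section 8.1, relatedness to the device is one of two conditions for entering the database at all, and not only something recorded about an event already entered. The amount of device differs by arm. Section 4.4 places randomisation in the operating room, and nothing in the documents provided describes an assessment of relatedness blind to arm.

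Consider a superficial infection that resolves without affecting pain, function or healing. After a graft, it can reasonably be called device related and entered. In a control, the same event may be called procedure related only, and Section 8.1 does not clearly require its entry. The opposite error is also possible: a reaction caused by the graft but judged unrelated to it, and not seen to affect an outcome, would be lost.

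At stake is how adverse event counts by arm will be read. Section 12 requires a final report and posting of results in a public database, and readers of a randomised trial will set the two arms side by side whether or not a test is planned. The MRI healing outcome is not affected.

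**Working it through.** **1. The reporting scopes side by side.**

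| Section | Events in scope | Is a procedure-related, non-serious event with no clear effect on an outcome covered? |
|---|---|---|
| 8.1, definition | Any undesirable experience, related or not | Yes |
| 8.1, entry rule | Device related, or affecting study outcomes | Not clearly |
| 8.1.1 | Serious events that are applicable (undefined) | No, concerns serious events only |
| 8.3 | Related events, graded for device or procedure | Yes, if related includes procedure |

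A site could follow 8.1 or 8.3 in good faith and enter different events.

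**2. Where the 8.1 rule depends on arm.**
- The outcome route does not mention the device and is open to both arms. Stiffness bears on range of motion, and many infections or nerve injuries would bear on pain, ASES or healing, so much of the important morbidity enters by this route.
- The device route is open in both arms but wider with DAA. Controls have repair anchors. DAA patients have the repair, the graft, the medial fixation and two lateral anchors. Section 8 does not say whether repair anchors count as the study device.
- What remains exposed is the group of procedural events that do not clearly affect an outcome.

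**3. What unequal capture does to the counts.** Let r be the true event rate, the same in both arms, and let c_T and c_C be the probabilities that an event is entered in the DAA and control arms.

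- Expected recorded events per arm = 60 × r × c
- Apparent rate ratio = (r × c_T) / (r × c_C) = c_T / c_C

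The 60 per arm is from Section 9.1. The documents give neither an event rate nor a capture probability, so r = 10% and the values of c are assumptions. With c_T = 1, expected DAA events are 60 × 0.10 = 6.

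| Control capture c_C | Expected control events | Apparent rate ratio | Spurious risk difference |
|---|---|---|---|
| 100% | 6.0 | 1.0 | 0 |
| 90% | 5.4 | 1/0.90 = 1.1 | 1.0 point |
| 75% | 4.5 | 1/0.75 = 1.3 | 2.5 points |
| 50% | 3.0 | 1/0.50 = 2.0 | 5.0 points |

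The ratio does not depend on r; the difference does. At 50% control capture it is 2.5 points for r = 5% and 10 points for r = 20%.

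**4. The other direction.** The same formula gives a ratio below 1 if capture is poorer with DAA: c_T = 75% and c_C = 100% gives 0.75. The documents do not settle which way the imbalance would go.

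**5. Could chance-level counts be misread?** With binomial counts at 60 per arm and r = 10%, take as the criterion that DAA shows at least 3 more events and at least twice the control count. The probability is 14% with equal capture, and 19%, 29% and 51% at control capture of 90%, 75% and 50%. With a Fisher exact p below 0.05 showing more events with DAA as the criterion, it goes from about 1% with equal capture to about 9% at 50%. The answer depends heavily on the chosen threshold and capture.

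**The case against.** The strongest reply is that this is a reasoned choice for a minimal-risk, post-market study of cleared products, and that the plan makes no safety comparison that could be biased. No safety objective or outcome is listed in Sections 3.3 and 3.4, and Section 9 plans no test or table of adverse events. Controls receive anchors, so they too can have device-related events. The outcome route applies equally to both arms and takes in much of what matters clinically. Section 8.3 mentions the procedure, which supports reporting procedural events in both arms, and the sponsor reviews assessments with a medical monitor for disagreements.

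Most of this stands, and it limits the point. A reader might infer that control events go unrecorded, or that a planned safety comparison is biased. The documents support neither: control capture is partial, and no comparison is specified. Nor does the 51% above measure the likely error. It is one scenario, with assumed half capture and a chosen threshold.

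Three parts of the reply do not dispose of the concern. Minimal risk justifies collecting less, but not collecting differently by arm. Sponsor review cannot recover events that were never entered, and it is not stated to be blinded. The wider wording in 8.3 does not override the restriction in 8.1; the two conflict.

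**Conclusion.** The point holds in a limited form. Followed as written, Section 8.1 allows the same procedural event to be entered in one arm and omitted in the other, and Sections 8.1.1 and 8.3 state different scopes. Recorded counts by arm could therefore be distorted in either direction for procedural events without a clear effect on outcomes.

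The size cannot be derived from the documents. The illustrative ratios of 1.1 to 2.0 rest on an equal true rate in both arms, full capture with DAA and control capture of 90% to 50%. With equal capture there is no distortion. It would be too strong to say that event rates cannot be compared at all: events that clearly affect outcomes are reportable in both arms.

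The healing analysis and the sample size are unaffected. This is a cheap improvement, worth making because Section 9 names safety data as a purpose of the sample and events not collected prospectively may be hard to recover.

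**What to change.** 1. In Section 8.1, replace the entry condition with one that is the same in both arms: all adverse events of the operated shoulder, all events possibly or probably related to device or procedure, and all serious adverse events. State how events graded unknown on the 8.3 scale are handled.
2. Keep relatedness as a recorded attribute of each event and not as a condition of entry.
3. Align Sections 8.1.1 and 8.3 with that rule, removing or defining the word applicable, and state what counts as the study device in each arm.
4. Add to Section 9 a descriptive table of adverse events by randomised arm, showing seriousness, severity and relatedness. No formal test is needed.

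The cost is a wording change and modestly more data entry at the sites. There are no added visits or procedures, and enrolment stays at 120.

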8.1.1 Serious Adverse Events

A serious adverse event is an adverse event that led to any of the following:

- death,
- serious deterioration in the health of a subject or user as defined by one or more of the following:
 - life-threatening illness or injury, or
 - a permanent impairment of a body structure or function
 - inpatient hospitalization or prolongation of existing hospitalization, or
 - medical or surgical intervention to prevent life-threatening illness or permanent impairment
- fetal distress, fetal death or a congenital anomaly or birth defect

All applicable serious adverse events will be reported by entering the event in the EDC as soon as possible and reported to the IRB/EC per their guidelines.

8.2 Non-reportable Events

Within the scope of this study, an AE does not include:

- Medical or surgical procedure (e.g., surgery, endoscopy, transfusion); the condition that leads to the procedure is considered an AE
- Pre-existing diseases or conditions present or detected at the start of the study that do not worsen
- Situations where an untoward medical occurrence has not occurred (e.g., hospitalizations for cosmetic elective surgery, social and/or convenience admissions)
- The disease or disorder being studied, or sign or symptom associated with the disease or disorder, unless the disease, sign or symptom is more severe than expected based on the subject's condition and/or requires intervention.

8.3 Adverse Event Documentation

The Principal Investigator or designee will report related adverse events for the study analysis. Adverse events will be evaluated and differentiated by:

- Severity of the event defined below.
 - Mild: Awareness of signs and symptoms, but easily tolerated; are of minor irritant type, causing no loss of time from everyday activities; symptoms would not require medication or a medical evaluation; signs and symptoms are transient.
 - Moderate: Discomfort severe enough to cause interference with usual activities; requiring treatment, but not extended hospitalization or intensive care for the subject.
 - Severe: Incapacitating with the inability to do work or normal activities; signs and symptoms may be systemic in nature or require medical evaluation and treatment; requiring additional hospitalization or intensive care (prolonged hospitalization).

- The following clarifications are provided for the serious adverse events:
 - Life-threatening means that the subject was, in the view of the Investigator, at immediate risk of death from the event as it occurred. The definition does not include an event that, had it occurred in a more severe form, might have caused death.
 - Hospitalization for elective treatment of a pre-existing condition that did not worsen during the study is not considered a serious adverse event.
 - “Inpatient” hospitalization means the subject has been formally admitted to a hospital for medical reasons. This may or may not be overnight. It does not include presentation at a causality or emergency room.
 - Important medical events that may not result in death, or be life-threatening, however, based upon appropriate medical judgment, may jeopardize the subject, and may require medical or surgical intervention to prevent one of the outcomes listed in this definition.
 - Is significant for any other reason.

- Relatedness to the device or procedure, defined as:
 - Unrelated: AE is due to the underlying disease state or concomitant medication, or therapy not related to the study-specific devices or procedures.
 - Probably not Related: AE had minimum or no temporal relationship to the study-specific devices or procedures, and more likely alternative etiology exists.
 - Possibly Related: AE had a strong temporal relationship to the study-specific devices or procedures and alternative etiology is equally or less likely compared to the potential relationship to the study-specific devices or procedures.
 - Probably Related: AE had a strong temporal relationship to the study-specific devices or procedures, and another etiology is unlikely.

Unknown: Relationship of the AE to the study-specific devices or procedures and alternative etiology is unknown.

